#### **HIV Care Providers/Clinical Staff**

Baseline/Month 1 is defined when the HIV care provider's first patient referred to the IC/ASA is enrolled into the study and receives their first study related injections of CABENUVA. HIV care providers/clinical staff will be asked to complete the Baseline/Month 1 questionnaire within 4 weeks of their first referred patient enrolled.

Month 4 and Month 8 assessments are to be completed when the HIV care provider's first referred patient completes the Month 4 or Month 8 study visits, respectively. Questionnaires and/or interviews can be completed up to 2 weeks before or after the Month 4 or Month 8 study visits

HIV Care Providers/ Clinical Staff Questionnaires	X (Within 4 weeks)		X		X	HIV care providers/clinical staff should complete questionnaires within 4 weeks following their first patient's enrolment into the study.
HIV Care Providers/ Clinical Staff Interviews					Х	Only HIV care providers/clinical staff that had patients enrolled into the study will be included in assessments post Baseline/Month 1.

#### Infusion Center Staff: Baseline questionnaires should be completed prior to the first participant enrolled

Baseline/Month 1 questionnaires should be completed prior to enrolment of the first participant at each infusion center.

Month 1 for each IC/ASA is defined when the first participant enrolls into the study at that specific IC/ASA and the participant is administered the first study related injections of CABENUVA.

Month 2 for potential interviews of approximately 5 IC/ASA staff will be defined after at least 1 participant, at their respective IC/ASA site, has completed their Month 2 study visits.

Month 3 and Month 8 will be defined after at least 1 participant, at their respective IC/ASA site, has completed their Month 3, or 8 study visits, respectively. Questionnaires and/or interviews can be completed up to 2 weeks before or after to the Month 3 or Month 8 study visits.

214747 Protocol Amendment 06

Procedure 	Baseline/			Treatme	ent Period (	Months)			E.D. 	Notes
Procedure.	Month 1 	2	3	4	5	6	7	8	E.D.	Notes
IC Staff Questionnaires	X (Prior to Month 1)		Х					Х		Month 1/Baseline questionnaires should be completed prior to the first participant enrolled at that IC/ASA.  Questionnaires at other months should be
										completed within $\pm$ 14 days of the scheduled month.
IC Staff Interviews		X						v		Month 1/Baseline questionnaires should be completed prior to the first participant enrolled at that IC/ASA.
IC Stall Interviews		^						X		Questionnaires at other months should be completed within $\pm$ 14 days of the scheduled month.

# **ANNEX 2. LIST OF STAND-ALONE DOCUMENTS**

Study Blueprint

Plan of Treatment (PoT)

Study Reference Manual (SRM)

#### **Annex 3: AE and SAE Definitions**

#### Annex 3.1 Definition of an Adverse Event

#### **AE Definition**

- An AE is any untoward medical occurrence in a clinical study participant, temporally associated with the use of CABENUVA, whether or not considered related to the CABENUVA.
- NOTE: An AE can therefore be any unfavorable and unintended sign (including an abnormal laboratory finding), symptom, or disease (new or exacerbated) temporally associated with the use of CABENUVA.

#### Definition of Unsolicited and Solicited AE

- An unsolicited AE is an AE that was not solicited and that is communicated by a
  participant or their legally authorized representative (LAR) who has signed the
  informed consent. Unsolicited AEs include serious and nonserious AEs. Only AEs
  that are considered related to CABENUVA or lead to discontinuation of
  CABENUVA will be recorded.
- Potential unsolicited AEs may be medically attended (i.e., symptoms or illnesses requiring hospitalization, emergency room visit, or visit to/by a healthcare provider). The participants or their LAR(s) will be instructed to contact the HIV care provider and/or the IC/ASA staff as soon as possible to report medically attended event(s), as well as any events that, although not medically attended, are of concern to the participant or LAR. Detailed information about reported unsolicited medically attended AEs will be collected by qualified IC/ASA site personnel, communicated to the HIV care provider, documented in the participant's source documentation, and recorded in the participant's records if related to CABENUVA or leads to discontinuation.
- Unsolicited AEs that are not medically attended nor perceived as a concern by participant or their LAR(s) will be collected during the visit with the participants or their LAR(s) and by review of available medical records at the next visit. Any unsolicited CABENUVA-related AEs reported during a visit must be documented in the participant's source documentation, communicated to the HIV care provider, and recorded in the eCRF by the IC/ASA if the event is considered related to CABENUVA or leads to discontinuation.

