#### 10.3.1. Specific Adverse Events to be Documented in this Study

Please refer to the most current USPIs for CABENUVA, VOCABRIA and EDURANT for additional safety information [CABENUVA USPI; EDURANT USPI, VOCABRIA USPI].

AEs and SAEs that are required to be recorded as defined in the eCRF include:

- AEs/Adverse drug reactions\* (ADRs) reported at the Baseline/Month 1 visit that are considered related to oral VOCABRIA or EDURANT or from the time of the last injections
- AEs/ADRs considered related to CABENUVA
- All AEs, whether considered related or not, that cause the participant to discontinue CABENUVA
- All SAEs whether related to CABENUVA or not
- All CV events listed in Annex 3
- COVID-19 related adverse events

Non serious AEs that are considered not related to CABENUVA or do not lead to withdrawal, should be documented in the source documents but will not be documented in the eCRF, as this information has been extensively collected in treatment clinical trials, no further information is needed to characterize these events.

\*An adverse drug reaction (ADR) is defined as a noxious and unintended response to a medication related to any doses where there is at least a reasonable possibility, or the relationship cannot be ruled out, that it is related to CABENUVA.

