#### **Events Meeting the AE Definitions**

 Any abnormal laboratory test results that are collected (hematology, clinical chemistry, or urinalysis) or other safety assessments (e.g., electrocardiogram (ECG), radiological scans, vital signs measurements) considered clinically significant and CABENUVA related in the medical and scientific judgment of the HIV care provider and/or IC/ASA physician.

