#### **AE Definition**

- Exacerbation of a chronic or intermittent pre-existing condition including either an increase in frequency and/or intensity of the condition. If the IC/ASA staff are alerted to this, these events should be recorded.
- New conditions detected or diagnosed after CABENUVA administration at the IC/ASA that are considered CABENUVA related or lead to the discontinuation of CABENUVA even though it may have been present before the start of the study.
- Signs, symptoms, or the clinical sequelae of a suspected CABENUVA interaction.
- Signs, symptoms, or the clinical sequelae of a suspected overdose of CABENUVA or a contraindicated or concomitant medication with the potential drug-drug interactions. Overdose per se will not be reported as an AE/SAE unless it is an intentional overdose taken with possible suicidal/self-harming intent. Such overdoses should be reported regardless of sequelae.
- The signs, symptoms, and/or clinical sequelae resulting from lack of efficacy will be reported as AE or SAE if they fulfil the definition of an AE or SAE. "Lack of efficacy" or "failure of expected pharmacological action" also constitutes an AE or SAE.

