# Annex 3.4 Recording and Follow-up of AEs and SAEs

# AE and SAE Recording

- When a CABENUVA-related AE, AE leading to withdrawal, or any SAE occurs, it is the responsibility of the HIV care provider to review all documentation (e.g., hospital progress notes, laboratory and diagnostics reports) related to the event.
- The IC/ASA will then record all relevant AE/SAE (VOCABRIA or EDURANT related AEs, CABENUVA-related AEs, AEs leading to withdrawal, all SAEs) information.
- If an event is not an AE per definition above, then it cannot be an SAE even if serious conditions are met (e.g., hospitalization for signs/symptoms of the disease under study, death due to progression of disease, etc.).
- It is **not** acceptable for the IC/ASA or HIV care provider to send photocopies of the participant's medical records to the Medical Monitor or the Sponsor in lieu of completion of the eCRF required forms.
- There may be instances when copies of medical records for certain cases are requested. In this case, all participant identifiers, with the exception of the participant number, will be redacted on the copies of the medical records before submission.
- The IC/ASA staff, working with the HIV care provider, will attempt to establish a diagnosis of the event based on signs, symptoms, and/or other clinical information. Whenever possible, the diagnosis (not the individual signs/symptoms) will be

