The seriousness of an AE will be independently assessed by the investigator from the severity of the AE. An SAE will be defined as any untoward medical occurrence that at any dose results in death, is lifethreatening, results in a congenital anomaly/birth defect, requires in-patient hospitalization or prolongation, or results in significant disability/incapacity. Important medical events that may not result in death, be life-threatening, or require hospitalization may be considered SAEs when, based upon medical judgment, they may jeopardize the participant and may require medical or surgical intervention to prevent one of the outcomes listed above. All SAEs will be presented in a table with the number and percentage of participants who experienced the event. The summary table will be displayed by SOC and PT.

Similarly, the following types of AE will be summarized in separate tables, if applicable:

- Baseline AEs reported at the Baseline/Month 1 visit beginning before informed consent and during the oral lead-in/injections that are considered related to oral CAB + RPV or the last CABENUVA injection
- Treatment-related AEs
- AEs leading to discontinuation
- Injection site reactions

- Cardiovascular events
- Liver monitoring/stopping events
- Pregnancy-related AEs
- COVID-19-related AEs

Other non-serious AEs that are considered not related to CABENUVA or do not lead to withdrawal are not documented in the eCRF, and therefore will not be summarized.

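### Annex 3.1 restricts recording of serious as well as non-serious AEs to related or discontinuation events, contradicting the all-SAE rule elsewhere in the protocol and the SAP

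*Protocol*

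**What the plan says.** Protocol Section 10.3.1 lists what goes into the eCRF. One item is "All SAEs whether related to CABENUVA or not"; all listed cardiovascular events and COVID-19 related AEs are separate items. The section then leaves out only non-serious events that are unrelated or do not lead to withdrawal. Sections 10.3.2, 10.3.5 and 10.3.10 (text and Table 3) require all SAEs to be reported within 24 hours.

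Annex 3.1, under the definition of unsolicited and solicited AEs, says: "Unsolicited AEs include serious and nonserious AEs. Only AEs that are considered related to CABENUVA or lead to discontinuation of CABENUVA will be recorded". Its next bullet covers medically attended events, with hospitalization as its first example. These are to be "recorded in the participant's records if related to CABENUVA or leads to discontinuation".

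The Annex's headline definition counts any untoward occurrence temporally associated with treatment as an AE, whatever its cause. Two later bullets add a condition. Laboratory and other safety findings qualify when "considered clinically significant and CABENUVA related in the medical and scientific judgment" of the provider or physician. The other bullet reads "New conditions detected or diagnosed after CABENUVA administration at the IC/ASA that are considered CABENUVA related or lead to the discontinuation of CABENUVA".

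Annex 3.4 tells the site to record all SAEs, and then adds: "If an event is not an AE per definition above, then it cannot be an SAE even if serious conditions are met". Annex 3.2 requires possible Hy's law cases to be reported as SAEs, with no reference to causality.

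The clinical SAP, Section 4.7.1.1, says: "All SAEs will be presented in a table with the number and percentage of participants who experienced the event". This is Table 14.3.10 in the SAP's list of tables.

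**The concern.** The sentence in Annex 3.1 is a recording rule. It names serious events as within its scope and then restricts what is recorded by causality or discontinuation. For an unrelated SAE in a participant who stays on treatment, a site cannot follow both this sentence and Section 10.3.1.

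Annex 3 is not an obscure place. Sections 10 and 10.3 send sites there for the definitions, and the reporting rule in Section 10.3.10 refers to it for SAEs. No clause says which text prevails. Detection, documentation and eCRF entry rest with staff at about 35 centers, so practice could differ by site.

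Two things depend on the answer: expedited SAE reporting, and the SAE counts in Table 14.3.10. The table could not reveal the problem, because an SAE never entered looks the same as an SAE that never happened.

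**Working it through.** The plan states no figure to reproduce. The check is to set the passages side by side and trace two test events through them.

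**Test event A: an unrelated hospitalization, treatment continued.**

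| Place | Outcome |
|---|---|
| Annex 3.1, headline definition | An AE, because causality is irrelevant |
| Annex 3.2 | Serious, because hospitalization is a criterion |
| Section 10.3.1 | Entered in the eCRF |
| Sections 10.3.2, 10.3.5, 10.3.10 and Table 3 | Reported within 24 hours |
| Annex 3.4, opening bullets | Recorded with all SAEs |
| Annex 3.1, unsolicited AEs | Not recorded, because neither related nor leading to discontinuation |
| Annex 3.1, medically attended events | Collected, sent to the HIV care provider and kept in source, but the further recording step does not apply |
| Clinical SAP 4.7.1.1 | Assumed to be in the data, since only non-serious unrelated events are expected to be absent |

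The two Annex 3.1 recording bullets stand alone against the rest.

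**Test event B: a possible Hy's law case judged to have another cause, treatment continued.**

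1. Headline definition: an abnormal laboratory finding can be an AE whatever its cause.
2. Laboratory bullet: the finding is not among those listed as meeting the definition, because it is not judged related.
3. Annex 3.4: what is not an AE cannot be an SAE.
4. Annex 3.2: the case must be reported as an SAE.

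Steps 2 and 3 lead one way, and steps 1 and 4 the other. A new serious illness judged unrelated meets the same conflict through the new-conditions bullet, without an express rule like step 4 to settle it.

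**Completeness of Annex 3.1.** Its recording sentence also omits the cardiovascular and COVID-19 events that Section 10.3.1 requires.

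**Size.** The documents give neither an expected SAE rate nor the share of SAEs judged unrelated, so the under-count cannot be derived. An illustration rests wholly on assumptions. Suppose S = 6 of 120 participants (6/120 = 5.0%) have one SAE each. Let a fraction u of those SAEs be unrelated and not lead to discontinuation, and a fraction f occur at sites that follow the Annex 3.1 sentence alone. Participants shown in the table = S × (1 − f × u).

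- f = 0: 6 × 1 = 6 (5.0%), no loss.
- f = 1, u = 0.80: 6 × 0.20 = 1.2 (1.0%).
- f = 1, u = 0.95: 6 × 0.05 = 0.3 (0.25%).

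The range runs from no loss to nearly complete loss. The documents say nothing about f.

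**The case against.** The best defense is that the protocol's intent is plain. The all-SAE rule appears in four body sections and again in Annex 3.4, whose grading text also covers any SAE. Section 10.3.12 makes every death an SAE. The Schedule of Activities sends sites to Section 10.3.10 for reporting requirements and to Annex 3 only for definitions. Section 10.3 offers a hotline for doubtful cases. Annex 3.1 itself keeps medically attended events in source and sends them to the HIV care provider, so a missed SAE would leave a trace. The SAE table is descriptive, and the study was not powered for safety.

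All of that stands, and it limits the point to a risk. It does not remove the conflict: Annex 3.1 still gives a contrary instruction and names serious events in doing so.

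A reader might go further and infer that relatedness has become part of the AE definition, so that an unrelated hospitalization is neither recordable nor an SAE anywhere in Annex 3. The documents do not support this. The headline definition disregards causality, the list of events not meeting the definition does not exclude unrelated ones, and Annex 3.4 calls for all SAEs. The two bullets conflict with the definition but do not replace it.

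A reader might also infer that causality is settled before the sponsor sees any event. Section 10.3.7 says otherwise: a causality assessment accompanies the initial SAE report, and the HIV care provider's view then determines the final one.

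**Conclusion.** The contradiction is real, and the text is wrong as written. Annex 3.1 applies to serious events a recording filter that the body of the protocol, Annex 3.4 and the clinical SAP confine to non-serious ones. Its laboratory and new-conditions bullets conflict with its own headline definition, and the laboratory bullet also conflicts with the Hy's law rule. Together with the statement that a non-AE cannot be an SAE, they leave room for misclassification.

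The consequence is possible under-recording of unrelated SAEs at any site that acts on the Annex 3.1 sentence, with an effect on 24-hour reporting and on Table 14.3.10. It is not certain, because most of the text requires all SAEs. A claim that the table would fall from 6 participants to about 0 or 1 would need the assumed rates above and every site ignoring the other sections; the documents support neither. The primary endpoint is not affected.

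**What to change.** Reconcile Annex 3.1 with Section 10.3.1:

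- Limit the recording sentence for unsolicited AEs, and the matching sentences in the two bullets after it, to non-serious AEs.
- State in the same place that all SAEs, and the cardiovascular and COVID-19 events listed in Section 10.3.1, are recorded whatever their relation to treatment.
- Remove the relatedness condition from the laboratory bullet, and the related-or-discontinuation condition from the new-conditions bullet, so that both match the headline definition. Section 10.3.1 then governs which non-serious events enter the eCRF.

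The cost is a wording change through the usual amendment and IRB route, and a memo to sites. No new data are required, because Section 10.3.1 already asks for every SAE, and the SAP needs no change.

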#### **Events Meeting the AE Definitions**

 Any abnormal laboratory test results that are collected (hematology, clinical chemistry, or urinalysis) or other safety assessments (e.g., electrocardiogram (ECG), radiological scans, vital signs measurements) considered clinically significant and CABENUVA related in the medical and scientific judgment of the HIV care provider and/or IC/ASA physician.

#### **AE Definition**

- Exacerbation of a chronic or intermittent pre-existing condition including either an increase in frequency and/or intensity of the condition. If the IC/ASA staff are alerted to this, these events should be recorded.
- New conditions detected or diagnosed after CABENUVA administration at the IC/ASA that are considered CABENUVA related or lead to the discontinuation of CABENUVA even though it may have been present before the start of the study.
- Signs, symptoms, or the clinical sequelae of a suspected CABENUVA interaction.
- Signs, symptoms, or the clinical sequelae of a suspected overdose of CABENUVA or a contraindicated or concomitant medication with the potential drug-drug interactions. Overdose per se will not be reported as an AE/SAE unless it is an intentional overdose taken with possible suicidal/self-harming intent. Such overdoses should be reported regardless of sequelae.
- The signs, symptoms, and/or clinical sequelae resulting from lack of efficacy will be reported as AE or SAE if they fulfil the definition of an AE or SAE. "Lack of efficacy" or "failure of expected pharmacological action" also constitutes an AE or SAE.

#### **Events NOT Meeting the AE Definition**

- Any clinically significant abnormal laboratory findings or other abnormal safety assessments which are associated with the underlying disease, unless judged by the HIV care provider to be more severe than expected for the participant's condition.
- The disease being studied or expected progression, signs, or symptoms of the disease/disorder being studied, unless more severe than expected for the participant's condition.
- Medical or surgical procedure (e.g., endoscopy, appendectomy): the condition that leads to the procedure is the AE.
- Situations in which an untoward medical occurrence did not occur (social and/or convenience admission to a hospital).
- Anticipated day-to-day fluctuations of pre-existing disease(s) or condition(s) present or detected at the start of the study that do not worsen.

#### Annex 3.2 Definition of an SAE

#### An SAE is defined as any serious AE that meets one of the following criteria:

#### • Results in death

#### • Is life-threatening

The term "life-threatening" in the definition of "serious" refers to an event in which the participant was at risk of death at the time of the event. It does not refer to an event that hypothetically might have caused death if it had been more severe.

#### An SAE is defined as any serious AE that meets one of the following criteria:

#### • Requires inpatient hospitalization or prolongation of existing hospitalization

- In general, hospitalization signifies that the participant has been admitted (usually involving at least an overnight stay) to the hospital or emergency ward for observation and/or treatment that would not have been appropriate in the physician's office or outpatient setting.
- Complications that occur during hospitalization are AEs. If a complication prolongs hospitalization or fulfils any other serious criteria, the event is serious. When in doubt as to whether "hospitalization" occurred or was necessary, the AE should be considered serious.
- Hospitalization for elective treatment of a pre-existing condition that did not worsen from baseline is not considered an AE.

# • Results in persistent or significant disability/incapacity

- The term disability means a substantial disruption of a person's ability to conduct normal life functions.
- This definition is not intended to include experiences of relatively minor medical significance such as uncomplicated headache, nausea, vomiting, diarrhea, influenza, and accidental trauma (e.g., sprained ankle) that may interfere with or prevent everyday life functions but do not constitute a substantial disruption.

## • Is a congenital anomaly/birth defect

#### Other situations:

- Possible Hy's Law case: alanine aminotransferase ≥ 3 x upper limit of normal (ULN) AND total bilirubin ≥ 2 x ULN (>35% direct bilirubin) or international normalized ratio (INR) > 1.5 must be reported as SAE
- Medical or scientific judgment should be exercised by the HIV care providers and/or the IC/ASA physician in deciding whether SAE reporting is appropriate in other situations, such as significant medical events that may jeopardize the participant or may require medical or surgical intervention to prevent one of the other outcomes listed in the above definition. These events should usually be considered serious.
  - o Examples of such events include invasive or malignant cancers, intensive treatment for allergic bronchospasm, blood dyscrasias, convulsions, or development of intervention dependency or intervention abuse.

